# 9.2 CHOICE Intervention GROUP

The DR-BNI intervention will take advantage of a "teachable moment" which is an opportunity created through dentist-parent/primary caregiver's interaction at the time of dental check-up where information about the health of their child's teeth is communicated (that is that their child has tooth decay). This can be used to encourage parents/primary caregivers to change unhealthy behaviours, especially when informed that their child has tooth decay. Up to 18 week window likely provides a teachable moment based on experience from our Dental RECUR trial so the DR-BNI intervention needs to be delivered within this timeframe however, the intervention should be completed within 12 weeks of randomisation. The intervention will primarily be delivered within the dental practice. If delivery face to face is prevented due to Covid-19 or a parent is unable to attend the practice for the intervention to be delivered, face-to-face (videocall) remote delivery online is allowed.

Participants randomised to the CHOICE Trial intervention will take part in a structured conversation (DR-BNI), lasting approximately 30 minutes, delivered by dental nurses using motivational interviewing with behaviour change techniques. It adopts a tailored and personalised approach taking account of parent/primary caregiver preferences for behaviour change. Three key dental behaviours (regular toothbrushing with a fluoridated toothpaste, sugar control and regular dental attendance) are communicated during an empathic and non-judgemental conversation and parents choose one or two behaviours they feel they can change for their child. These are set as goals that are specific, measurable, attainable, relevant and time-based (SMART) and aim to promote oral health. The intervention is delivered in six steps, each lasting around five minutes covering:

- 1. **Build Rapport.** Get the parent/primary caregiver's agreement to talk about the child's dental decay. Talk about the possible causes of tooth decay and ask which are the most relevant to their child.
- 2. **Pros and Cons.** Review child's oral health behaviours (e.g., sugar intake, brushing with fluoride toothpaste, regular dental attendance). Highlight discrepancies.
- 3. **Feedback.** Assess parent/primary caregiver knowledge, elicit permission, provide evidenced-based information about tooth decay.
- 4. **Readiness to Change.** Explore readiness to change using resources and offer information

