- 5. Action Plan. Negotiate a goal and summarise discussion. Develop a plan of action/prescription for change based on parent/primary caregiver's ideas.
- 6. **Thanks, Summarise, and Feedback.** Summarise discussion, outline next steps, provide feedback questionnaires.

In the general dental practice setting, the trained dental nurses will meet with each parent/primary caregiver assigned to the intervention arm of the trial for the structured 30-minute conversation outlined above.

The dental nurses who deliver the intervention will have training provided by the CHOICE trial team. Dental nurses will attend a one-day workshop (in person or online) to learn how to deliver DR- BNI. The DR-BNI is a complex, multi-faceted and tailored intervention that requires training of the dental nurses in its discrete components as well as its unique philosophy and this is not routinely practiced in dentistry. Training is led by an independent experienced practitioner psychologist trained in motivational interviewing and behaviour change techniques.

Training will be theory and skills-based teaching including theory of behaviour change, practical motivational interviewing skills essential to deliver the DR-BNI intervention, and role-play/practice with supervision and feedback. The aim of the DR-BNI intervention is to focus on a forward and future based perspective where dental caries can be prevented in the future rather than dwelling on the past, which cannot be changed. Dental nurses will be expected to practise their skills following the training with a peer, who has also been trained, and provide one recording for fidelity check prior to delivering their first intervention. Training will be supported by a DR-BNI dental practice toolkit including a dental nurse intervention manual/video and patient facing materials which will be take-home resources given to participants by the dental nurses that reinforces goals and action planning for behaviour change.

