#### • Timing of the intervention

- Once the research team are made aware of the group allocation, participants (parent/primary caregiver) will receive their allocated intervention ideally within 6 weeks of randomisation but no longer than 12 weeks after. This will be administered as described in Section 9.
- Delivering DR-BNI in a comprehensible way
It is recognised that some parents/primary caregivers may need the support of interpreters to ensure that the intervention, DR-BNI, can be received in a comprehensible way. If required, sites should follow standard NHS procedures to book an interpreter to ensure that eligible families are not excluded from participation in the CHOICE trial.

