### 10.8.8 Health Economic Assessments

Utilization of care will be taken from clinical records and monetised using the Northern Ireland Statement of Dental Remuneration for care provided by the GDP and from National Cost Collections for hospital provided extractions. These costs will be aggregated over the 24-month study period in the base case analysis (and over 10 years in the follow-up study). To these will be added the cost of the intervention for the intervention group. Intervention costs will be based on nurse delivery time as recorded by the providing nurse and monetised using agenda for change pay rates for a dental nurse at band 2 in the base case analysis. As a validation exercise a random sample of intervention delivery times will be timed by the research team and compared with those reported by nurse providers. Incremental costs in the base case analysis will be based on differences in costs over 24 months between the control and intervention group. As a range of outcomes are captured in the study including the proportion who accumulate additional caries, the number of fillings provided, episodes of pain and quality of life (QOL) measures, a range of incremental effects will also be calculated based on differences in these at 24 months. Where appropriate, for example in respect of quality of life, incremental effects will be based on differences in the change in QOL between baseline and follow-up between intervention and control groups.

Mean differences in cumulative discounted costs and effects between the intervention and control groups will be described and tested using standard parametric approaches to examine differences in mean costs, proportion of children whose caries progress, episodes of pain, fillings and health-related quality of life etc. A series of incremental

cost effectiveness ratios will be estimated detailing the difference in cost divided by the difference in effect between intervention and control groups. To take account of the possibility that costs, and effects are jointly distributed, uncertainty around ICERs will be explored in deterministic models using a nonparametric bootstrapping approach and uncertainty around the willingness to pay for outcomes using cost effectiveness acceptability curves.

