## 13.7 Health Economic Analysis Plan

A full economic analysis plan (EAP) will be written prior to the conduct of any comparative analysis of the treatment arms. The main features of the EAP are summarised below:

Participants will be included in the analysis set based on the intention-to-treat principle.

Resource related to dental treatments will be taken from routine administrative claims data for the 24 months of the trial and subsequently for the 10 year follow-up. Treatments will be measured and monetised using the statement of dental remuneration for those delivered in the community and standard references for those delivered in secondary care. Where missing data exists multiple imputation methods will be used to estimate missing values. Intervention costs will be added to treatment costs for the intervention group.

Resource use and costs will be reported for the intervention and control groups at 24 months and 10 years using mean, median and standard deviations. Outcomes will be similarly reported at 24 months and for selected outcomes at 10 years. Differences in mean cost and outcomes between groups will be estimated and reported using t-tests. Differences in cumulative care costs over 24 months will be related to differences in effects as cost-effectiveness ratios following a bootstrapping exercise to take account of potential joint distributions between costs and outcomes. Sub-group analysis related to socio-economic status and ethnicity will be explored based on partitioned samples. Seemingly unrelated regression analyses will be used as an adjunct to the bootstrapping exercise and covariates for socio-economic status and ethnicity entered as covariates.

Sensitivity analysis, to include variation in specific elements of cost – for example based on the time and motion study of intervention delivery time – will be undertaken as will a probabilistic sensitivity analysis.

To take account of potential spill-overs related to sibling use of services, routine administrative data on dental service use by siblings aged <11 at the time of the study child's recruitment will be secured. Their use of services will be used to estimate spill-over costs and their outcomes measured or where unobserved estimated based on relationships between costs and outcomes for study children. Spill-over costs and outcomes will be added to those of the study child in sensitivity analysis at 24 months and 10 years.

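### The base-case intervention cost counts only the nurse's delivery time, which understates incremental cost in favour of DR-BNI; separately, quality-of-life effects are taken as change scores, which costs precision

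*Protocol*

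**What the plan says.** **Cost.** Section 10.8.8 of the protocol gives the costing rule: "Intervention costs will be based on nurse delivery time as recorded by the providing nurse", "monetised using agenda for change pay rates for a dental nurse at band 2 in the base case analysis". It names no other component. Section 13.7 adds intervention costs to treatment costs in the DR-BNI arm without widening that definition.

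Section 9.2 describes what delivery requires. The session is a conversation "lasting approximately 30 minutes, delivered by dental nurses using motivational interviewing with behaviour change techniques". On training it says: "Dental nurses will attend a one-day workshop (in person or online) to learn how to deliver DR- BNI". A practitioner psychologist leads the workshop. Each nurse then practises with a trained peer and submits a recording for a fidelity check before the first session. Practices receive a toolkit, families receive take-home resources, and nurses whose recordings fall short receive further supervision. For parents who need language support, Section 10.6 says "sites should follow standard NHS procedures to book an interpreter".

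The one-way sensitivity analyses named in Section 10.8.8 cover unit costs, the discount rate and session length. Section 13.7 gives the timing study of delivery as its example. Both sections add a probabilistic sensitivity analysis.

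**Quality of life.** Section 10.8.8 says that, where appropriate, "incremental effects will be based on differences in the change in QOL between baseline and follow-up". Section 13.7 says: "Differences in mean cost and outcomes between groups will be estimated and reported using t-tests". ICER uncertainty comes from a nonparametric bootstrap and acceptability curves. Seemingly unrelated regression, with socio-economic status and ethnicity as covariates, is an adjunct.

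**The concern.** A nurse cannot deliver DR-BNI without the training, and Section 9.2 itself says that dentistry does not routinely practise it. The control arm incurs none of this for DR-BNI, so these costs do not cancel in the increment. (The free dental pack goes to both arms and does cancel.) The omission therefore works in one direction: it lowers incremental cost and makes every ICER and acceptability curve look better for DR-BNI. Varying session length or pay rates cannot expose a component that was never in the cost.

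The quality-of-life point is smaller and of a different kind. Baseline EQ-5D-Y and caregiver-questionnaire values are collected, and Section 13.6 already adjusts the parent-reported secondary outcomes for site and baseline value. Using change scores in the economic analysis gives up precision that the trial could have at no extra data cost.

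**Working it through.** **Caseload.** Section 13.2.1 states 363 evaluable children per group for a 12-point difference, 90% power and alpha 0.05. It gives no control rate for CHOICE. With two-sided alpha, n = [1.96·√(2p̄(1−p̄)) + 1.2816·√(p1(1−p1) + p2(1−p2))]² / (p1−p2)². At 56% v 44% this is (1.3859 + 0.8997)²/0.0144 = 362.8, so 363. 55% v 43% also gives 363, and 62% v 50% gives 358. Then 363/0.80 = 453.75, so 454 per group and 908 in total. The stated figures reproduce.

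With 40 practices, intervention children per practice = 454/40 = 11.35. Costed delivery time per practice = 11.35 × 30 = 340.5 minutes, about 5.7 hours.

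**Workshop time per child.** Assumptions: one nurse per practice (the stated minimum) and a working day of 6 to 8 hours (the protocol says one day).

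| Training time | Spread over | Added minutes per child | Share of nurse time (workshop + session) left uncosted |
|---|---|---|---|
| 6 h | 11.35 children | 360/11.35 = 31.7 | 31.7/61.7 = 51% |
| 7.5 h | 11.35 children | 450/11.35 = 39.6 | 39.6/69.6 = 57% |
| 8 h | 11.35 children | 480/11.35 = 42.3 | 42.3/72.3 = 59% |
| 7.5 h | 50 children | 450/50 = 9.0 | 9.0/39.0 = 23% |
| 7.5 h | 100 children | 450/100 = 4.5 | 4.5/34.5 = 13% |
| 7.5 h | 200 children | 450/200 = 2.25 | 2.25/32.25 = 7% |

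Two trained nurses per practice would double the added minutes: 63 to 85 at the trial caseload. Trainer time, materials, supervision and interpreters come on top. The protocol gives no figures for them, so no monetary effect on the ICER can be computed.

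**Change score against baseline adjustment.** With equal variance s² at baseline and follow-up and correlation rho, the per-child variance is 2s²(1−rho) for a change score and s²(1−rho²) for a baseline-adjusted comparison. The ratio is 2/(1+rho). The protocol does not give rho, so the range is assumed. The evaluable total is 2 × 363 = 726.

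| rho | Variance ratio | CI wider by | 726 children act like |
|---|---|---|---|
| 0.3 | 2/1.3 = 1.54 | 24% | 726 × 0.65 = 472 |
| 0.5 | 2/1.5 = 1.33 | 15% | 726 × 0.75 = 544 |
| 0.7 | 2/1.7 = 1.18 | 8% | 726 × 0.85 = 617 |

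A simulation with 4,000 trials of 363 per arm and a true effect of 0.200 gave mean estimates of 0.197 to 0.200 for change scores and 0.198 to 0.199 for baseline adjustment. The standard-error ratios were 1.22, 1.15 and 1.08. So precision is lost but no bias appears.

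**The case against.** The strongest reply is that Sections 13.1 and 13.7 promise a full economic analysis plan, and that cost components and covariates normally sit there. That would answer a silent protocol, but Section 10.8.8 states a base-case rule, and the rule is too narrow. A second reply is that the sensitivity lists are open-ended. That is right: training and materials are not excluded. They are simply not named, so nothing in the text commits the analysis to restoring them. A third is that some fidelity checking serves the process evaluation and is research cost, and that interpreters are needed only for some families. Both parts stand and limit what belongs in the base case.

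Four stronger readings are tempting, and the documents do not support them.

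- A reader might infer that change scores bias the ICER. Allocation is randomised 1:1, so they do not; the bias lies in the costs. Against unadjusted 24-month values, a change score is even the more precise choice when rho exceeds 0.5.
- A reader might infer that t-tests drive ICER uncertainty. They report mean differences; ICER uncertainty comes from the bootstrap.
- A reader might infer that the economic analysis departs from Section 13.6 by ignoring age. Age is a randomisation stratum in Section 13.3.1, but Section 13.6 adjusts for site and baseline only.
- A reader might take 57% of nurse time as a minimum uncosted share. It is 51% with a 6-hour day and about 23% to 7% when a 7.5-hour day is spread over 50 to 200 children. It is also a share of nurse minutes, not of incremental cost.

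**Conclusion.** The costing point holds. As written, the base case prices delivery minutes only and understates the incremental cost of DR-BNI. The size depends on a caseload that the costing text never states. With one nurse per practice, the workshop adds about 32 to 42 minutes per child at the trial caseload, at least as much as the 30 costed, but only 9.0 to 2.25 minutes if a 7.5-hour day serves 50 to 200 children. The other components add an amount that cannot be quantified from the protocol.

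The quality-of-life point holds as a loss of precision only: a variance ratio of 1.54 to 1.18 for assumed rho of 0.3 to 0.7. It affects ICERs based on quality of life, not those per caries case, filling or pain episode. Both points should be corrected; neither touches the clinical primary analysis.

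**What to change.** In Sections 10.8.8 and 13.7, define the base-case intervention cost as delivery time plus:

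- nurse and trainer time for training, spread over a stated caseload or useful life;
- the practice toolkit and take-home materials;
- the supervision that routine delivery would need;
- interpreters for the DR-BNI session.

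Exclude fidelity work done only for research. Name the training caseload and each of these components in the sensitivity analyses. Interpreter use is not among the items listed for recording at the intervention visit (Sections 10.6 and 10.8), so check that it will be captured.

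For quality of life, replace change scores and t-tests by regression of the 24-month value on arm, baseline value and site. Use that model within the bootstrap, and add the same covariates to the seemingly unrelated regression.

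The cost is a wording change, a little more costing work and a somewhat less favourable ICER. The baseline quality-of-life data are already collected.

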## **10.9 Intervention Discontinuation and Participant Discontinuation/Withdrawal**

In consenting to the trial, parents/primary caregivers agree to all trial activities including administration of the trial intervention and follow-up assessments and data collection. Every effort should be made to facilitate the completion of these for every recruited participant. If it is not possible to complete these activities (or it is deemed inappropriate) the reasons why should be documented. The following sub-sections describe the different levels of discontinuation/withdrawal.

## 10.9.1 **Premature Discontinuation of Trial Intervention**

Participants may discontinue the intervention for reasons including, but not limited to:

- Participant-led i.e., request by the participant or parent/caregiver
- Insufficient time to complete the intervention
  - Discontinuation from trial intervention does not mean discontinuation of the trial altogether, and the remaining trial procedures, follow up assessment and data collection should be completed as indicated in the protocol (unless consent is specifically withdrawn, see section 10.9.3). Intervention withdrawal should be recorded on the trial database.

### 10.9.2 Participant Withdrawal

Persons with parental responsibility are free to withdraw consent for them/their child at any time without providing a reason. If consent is withdrawn for the trial, data will be collected up to the point of that withdrawal of consent and included in the analyses. The participant will not contribute further data to the trial and the Withdrawal eCRF should be completed.

If a participant withdraws from the ENCOURAGE sub study or the CHOICE study then no further saliva samples will be collected. If any samples have already been collected, the samples will continue to be stored. Should a participant wish for a sample to be destroyed then they can request this and this will be made clear in the Patient Information Sheet.

Any SAEs will be notifiable to the LCTC via processes detailed in Section 12 even if a participant has withdrawn from follow up.

### 10.9.3 Loss to Follow-up

A participant will be considered lost to follow up if they fail to attend the final dental assessment as discussed in section 10.7.

Contact details (telephone number and/or email address and/or postal address) will be collected at the baseline visit, and entered into a restricted-access area of the trial database to allow telephone follow-ups to occur.

**N.B.** Postcode will be collected for all participants, where possible, to be able to derive IMD.

Data collection with NHS Digital, NHS BSA, BSO and PAS will continue, if consented at baseline, unless the participant confirms that they would like to withdraw consent.

## 10.10 End of Trial

The end of the trial is defined to be the date on which data for all participants is frozen and data entry privileges are withdrawn from the trial database. The trial may be closed prematurely by the Trial Steering Committee (TSC), on the recommendation of the Independent Data and Safety Monitoring Committee (IDSMC).

Site and closure activities will be centrally coordinated and conducted in accordance with LCTC processes regardless of whether the trial closes as planned or prematurely. This includes activities such as:

- End of Trial notification to REC
- Trial-related materials reconciled and returned/disposed of as appropriate
- All site data entered onto the study database, discrepancies raised, and satisfactory responses received
- Quality Control checks of the Investigator Site Files and Trial Master File as appropriate.

### 10.10.1 **Study Discontinuation**

In the event that the study is discontinued, there are no considerations for continuation of allocated treatment as this occurs only once following randomisation.

# **11 SUB-STUDIES/NESTED STUDIES**

# 11.1 Study Within A Trial (SWAT)

## 11.1.1 Rationale

Achieving recruitment targets and widening access for all eligible participants is a common challenge in dental clinical trials (Robinson et al., 2016). Therefore, we plan to put in place additional measures (Motivational Letter vs Motivational Letter and Family Oral Health Toolkit) from the outset of the recruitment to the CHOICE trial and we will evaluate the value of these measures alongside the trial.

Widespread and effective long-term screening of children's oral health in school is not undertaken in England and Northern Ireland (Arora et al., 2019, Milsom et al., 2006). In England, biennial surveys of the dental health of 5year-olds are conducted to a national protocol and co-ordinated by Public Health England. From 1985-2007, these surveys were conducted under a nationally co-ordinated programme in which children were examined under a passive consent process, that is, an information letter was sent to parents advising of the survey with the ability to withdraw their child, but explicit parental consent was not sought. During these times, participation rates were 75% and above. From 2007/08, guidance from the Department of Health changed to a requirement for positive parental consent for dental surveys (Davies et al., 2011).

The process of recruitment to screening of children's oral health has been unchanged and remains to be by letter to parents through schools, with one reminder advised. To undertake the dental examination, a signed return is required from parents. The percentages of parents of 5-year-olds consenting and whose children received dental examinations for the National Dental Epidemiology Programme in 2017 were: Essex 52%; Liverpool 51% and Leeds 56%. Only 6% of parents declined to participate, and absenteeism on the day of examination was low at 3%; the most common reason for non-participation was non-response (32%; ) (Public Health England, 2017). When this change to parental consent was introduced, studies were conducted to compare strategies for maximising consent rates for these dental surveys but found no differences and concluded that further research was needed (Glenny et al., 2013). A range of strategies had been identified through study and review, namely: greater promotion of the surveys to school heads, teachers, parents and pupils; having reminder contacts; and having a member of the survey team coordinate and closely monitor the recruitment process (Robinson et al., 2016).

Taking the above into account, recruitment of the target population to clinical trials is particularly challenging especially when reaching diverse communities. A systematic review of studies exploring recruitment and retention to RCTs involving children identified several barriers (Robinson et al., 2016). These included younger parents, those from a low SES and ethnic minority background as well as those who had completed less education. While the systematic review did not find consensus across studies meaning that these characteristics do not necessarily predict recruitment and retention into RCTs, they did recommend exploring the process of participation for such families. We recognise the challenges to recruitment to the trial such that many children who develop dental caries have sporadic attendance at dental practice and often only attend when acute problems arise resulting in limited treatment options.

